6. The PK/PD, ADA, correlative blood sample collection: 2x 10ml EDTA samples at each time point. The samples should be collected pre-dosing and 30±10 min after each IV infusion. Sample collection must be from the opposite arm to that used for study drug infusion.
7. Women of childbearing age only

[figure not shown]
Figure 2: Phase II Randomized, Placebo Controlled Study Schema

Table 2. Flow Chart for Phase II Study (CD24Fc Group vs Placebo Group)

CD24Fc 480 mg on day 1, 240 mg on day 14, and 240 mg on day 28 i.v. (a total course=28 days)							
Trial Period	Screening	Treatments			Post-Treatment	End of Study	Post-Study
Dose/Treatment Number		1	2	3	2-week Evaluation	Safety Follow Up	Survival Follow Up
Day	-14 to -1	1	14 ± 3	28 ± 3	42 ± 3	60 ± 3	Every 3 months to 1 year ¹
Drug Dispensation							
CD24Fc		X	X	X			
Placebo		X	X	X			
Administrative Procedures							
Eligibility evaluation, informed consent, medical history	X						
Medication review	X	X	X	X	X	X	X
Post-study status, survival status							X
Clinical Procedures							
Full physical exam	X				X	X	
Directed physical exam		X	X	X			
ECOG PS, vital signs, EKG ² , acute AE monitoring ³	X	X	X	X	X	X	
Evaluation for ICI retreatment					X		
Toxicity assessment (NCI CTCAE V5.0)	X	X	X	X	X	X	X ⁴
Laboratory Procedure/Assessment							
CBC with differential, CMP	X	X ⁵	X ⁵	X ⁵	X	X	
Correlative blood and plasma sample collection, PK/ADA samples ⁶		X ⁶	X ⁶	X ⁶	X	X	
Pregnancy test (urine or serum b-HCG) ⁷	X						

1. Frequency of follow-up office visits at the discretion of treating physician. Chart check every 3 months for post treatment and survival status. To continue until death or up to 1 year after completion of the study.
2. On days of CD24Fc administration, vitals and EKG will be obtained prior to and post infusion of study drug.
3. All patients will be monitored for 1-hour post infusion with a registered nurse or nurse practitioner within immediate proximity.
4. If irAE has not resolved to ≤grade 1 at day 60, check on primary oncologist's document for the grade of AE at every visit until resolution.
5. CBC and CMP blood draw should be within 3 days prior to CD24Fc administration
6. The PK/PD, ADA, correlative blood sample collection: 2x 8 ml EDTA samples at each time point. For all infusions, the samples should be collected pre-dosing and 30±10 min after IV infusion and the end of study visit. Sample collection must be from the opposite arm to that used for study drug infusion.

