4. TOXICITIES MONITERED

4.0 Treatment-Related Toxicities

The toxicity scale, definitions, and specific criteria for each toxicity level will be those as outlined in the guidelines defined by the NCI CTCAE version 5.0. ([Appendix 4](#)). If the patient develops any grade 3 or greater hematologic or non-hematologic toxicity that is possibly, probably, or definitely related to the CD24Fc, no further drug administration will be given to that patient and the patient will be removed from protocol therapy (see Section 4.1). Treatment delay within 3 scheduled days is allowed. Dose modification based on the renal and hepatic function values and hematologic laboratory values (see Section 6.4).

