4.1 Phase I Dose Limiting Toxicities

- 1) Grade 4 non-hematologic toxicity (not laboratory).
- 2) Grade 4 hematologic toxicity including Grade 4 neutrophil count decrease, Grade 4 platelet count decrease or Grade 4 anemia regardless of duration.
- 3) Grade 3 Neutrophil count decrease lasting > 1 week, or febrile neutropenia.
- 4) Grade 3 Platelet count decrease lasting > 1 week, or Grade 3+ thrombocytopenia with bleeding.
- 5) Grade 3 non-hematologic toxicity (not laboratory) will be considered a DLT with the following exceptions: grade 3 fatigue, Grade 3 nausea, vomiting, or diarrhea lasting < 72 hours, (Grade 3 nausea, vomiting, or diarrhea lasting >72 hours despite optimal supportive care is a DLT).
- 6) Any Grade 3 non-hematologic laboratory value if:
 - Associated with clinical symptoms or signs, or
 - Medical intervention is required to treat the patient, or
 - The abnormality leads to hospitalization, or
 - The abnormality persists for >1 week.
- 7) AST and/or ALT elevation >20 x ULN with concurrent total bilirubin elevation to >5 x ULN

without initial evidence of cholestasis.

8) Grade 5 toxicity (i.e., death).

The treatment related toxicities should be evaluated as CD24Fc treatment emergent AE that is not associated to irAEs defined in enrollment. The DLT monitoring period is the 14 days after the first dose of CD24Fc at 480 mg. If DLT occurred in 2 patients during the first dose of CD24Fc dosing in the 14-day period, CD24Fc will be reduced to 240 mg as first dose, or 120 mg until no more than 1/6 patients developed DLT. The study will be terminated if >2 patients have DLT at this reduced dosing. In Phase I, patients will be dosed at least two hours apart and no more than two patients will be enrolled in the same day.

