6.1.1 Phase II Randomized Double Blind Placebo Controlled Study

Phase II study will consist of a randomized double blind placebo controlled study involving patients who have treatment interruption due to grade 2 or 3 irAEs. Patients may receive steroids at the discretion of the treating physician prior to and during treatment with CD24Fc. As the steroids is the most commonly used SOC therapy for irAEs and it affects the severity and duration of irAE, we will separate the subjects into two groups based on the status of steroids use at registration. Each group of patients will be randomized (1:1) to receive CD24Fc vs placebo in addition to SOC treatment for irAE. Patients who are randomized to treatment with CD24Fc will receive treatment every 2 weeks for total of three treatments. Placebo group will receive 100 mL of normal saline every 2 weeks for total of three treatments. Refer to [Table 2](#) and [Figure 2](#) for treatment schedule. All patients shall complete 3 treatments.

Two weeks after completing the third treatment dose, patients will be re-evaluated for retreatment with ICI at the discretion of the treating physician and post treatment re-evaluation. Thereafter, patients will continue to end of treatment safety follow up on day 60. After the end of treatment, we will follow patients with irAE and survival by chart check every 3 months for up to 1 year.

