6.4.3 Dose adjustment

There should be a one level dose reduction (i.e., CD24Fc 240 mg on day 1, 120 mg on day 14, and 120 mg on day 28 i.v.) if any \geq G3 hematologic due to CD24Fc that requires < 2 week to recover to grade 1 or less. There will be no dose reduction according to irAEs.

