6.6 Toxicity

A brief written summary documenting the toxicity or adverse reactions after the 6th patient (phase I study) has received his/her 3th dose will be prepared with input from the UCD clinical PI. The brief report will summarize and define if the study should continue or be terminated. At the end of Phase II study, a summary will likewise be completed to address the same issues. A recommendation whether to continue onto a Phase II clinical trial will also be included.

Toxicity assessments will be done by the treating physician or their licensed representative (such as nurse practitioner) on the days of therapy.

Patients with progressive disease will be counseled as to the option of exiting the study. They will be advised on their disease progress and future options, and their response, if any, to the therapy.

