6.7 Criteria for Removal from Protocol Treatment

- Unacceptable toxicity (as determined by the treating physician and/or the patient), or toxicity requiring discontinuation of treatment (See sections 4.0 and 4.1).
- Elevation in AST or ALT $>20x$ ULN on bloodwork prior to CD24Fc treatment.
- Elevation of total bilirubin $>5x$ ULN on bloodwork prior to CD24Fc treatment.
- If the recovery of any $\geq G3$ hematologic or non-hematological toxicity due to CD24Fc to grade 1 or less requires > 2 weeks.
- Patients may choose to withdraw from the study at any time for any reason.
- Patients may be withdrawn from the protocol at the investigator's discretion if the investigator feels that continuation is not in the patient's best medical interest or if the patient is non-compliant with treatment.
- Completion of treatment CD24Fc.
- All reasons for discontinuation of treatment must be documented in the case report forms.
- Therapy after Protocol Treatment is stopped: If patients fail to respond to the protocol treatment and/or are removed from the therapy because of toxic effects or "disease progression", further treatment, if any, is at the discretion of the investigator.

Follow-up off Protocol Treatment: After removal from protocol treatment, all patients will be followed for late toxicities. Patients will be seen 4 weeks, 4 months and 7 months after coming off therapy. If ongoing toxicities have not resolved to \leq grade 1 within the first 4 weeks, patients are to be seen every month until toxicity resolves to \leq grade 1. No new toxicities after the 4-week follow-up will be re-reported unless considered related to protocol treatment by the investigator.

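### Sections 4.0 and 6.4.3 give opposite orders for related grade 3 or higher hematologic toxicity; separately, a first dose reduced in Phase I is not carried into the Phase II text

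*Combined protocol and SAP*

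**What the plan says.** On toxicity in an individual patient, three sections apply.

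- Section 4.0 covers any grade 3 or higher toxicity, hematologic or not, judged at least possibly related to CD24Fc: "no further drug administration will be given to that patient and the patient will be removed from protocol therapy". It then points to 6.4 for dose modification on renal, hepatic and hematologic laboratory values.
- Section 6.4.3 orders a one-level reduction, to 240/120/120 mg, for a grade 3 or higher event that is "hematologic due to CD24Fc that requires < 2 week to recover to grade 1 or less".
- Section 6.7 lists removal where recovery of a grade 3 or higher "hematologic or non-hematological toxicity due to CD24Fc to grade 1 or less requires > 2 weeks". Its first bullet also sends the reader back to 4.0 and 4.1.

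On the dose level for the trial, section 4.1, headed Phase I, says: "The DLT monitoring period is the 14 days after the first dose of CD24Fc at 480 mg". If 2 patients have a DLT in that window, "CD24Fc will be reduced to 240 mg as first dose, or 120 mg until no more than 1/6 patients developed DLT". For Phase II, section 6.1.1 says "Patients who are randomized to treatment with CD24Fc will receive treatment every 2 weeks for total of three treatments" and refers to Table 2 and Figure 2 for the schedule. The header of Table 2 reads "CD24Fc 480 mg on day 1, 240 mg on day 14, and 240 mg on day 28 i.v. (a total course=28 days"). After Phase I, section 6.6 calls for a toxicity summary: "The brief report will summarize and define if the study should continue or be terminated".

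**The concern.** The main issue is that the same event triggers two incompatible orders. Two investigators who both follow the protocol could act in opposite ways on the same related grade 3 neutrophil fall. One would stop the drug and take the patient off therapy; the other would give reduced doses. This can happen in either phase and does not depend on how Phase I turns out.

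The secondary issue arises only if Phase I meets its reduction trigger. Phase I would then have moved to a lower first dose, while the visible Phase II instructions would still order a 480 mg first dose. That is 2 times the 240 mg level and 4 times the 120 mg level, for a planned arm of 36 patients.

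**Working it through.** The plan gives no figure of its own on either point. The check is a comparison of the rules, plus simple arithmetic.

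**1. Do 4.0 and 6.4.3 cover the same event?** An event due to CD24Fc (6.4.3, 6.7) lies within the at-least-possibly-related range of 4.0, so attribution does not separate them. For a related hematologic event:

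| Event | 4.0 | 6.4.3 | Two-week criterion in 6.7 |
|---|---|---|---|
| Grade 3, recovery under 2 weeks | stop and remove | reduce one level | not met |
| Grade 3, recovery in exactly 2 weeks | stop and remove | silent | not met |
| Grade 3, recovery over 2 weeks | stop and remove | silent | remove |
| Grade 4, recovery under 2 weeks | stop and remove | reduce one level | not met |

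Rows 1 and 4 are direct contradictions. If 4.0 governs, 6.4.3 can never operate and the two-week criterion in 6.7 is redundant; that criterion also covers non-hematologic toxicity, so it is redundant there too. If 6.4.3 governs, 4.0 is wrong for these events. Row 2 falls under neither 6.4.3 nor the two-week criterion.

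**2. Drug still to be given.** The reduced level in 6.4.3 is 240/120/120 mg.

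- After dose 1: 0 mg under 4.0; at most 120 + 120 = 240 mg under 6.4.3.
- If counts are below the 6.4.2 thresholds at Day 14 and do not recover within the 3 days allowed by 6.3, that dose is omitted and at most 120 mg remains.
- After dose 2: 0 mg under 4.0; at most 120 mg under 6.4.3, and 0 mg if the Day 28 dose is also omitted.

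The Day 1 dose listed in 6.4.3 has already been given to any patient to whom the rule applies.

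**3. Carry-forward of a reduced first dose.** Section 4.1 can lower the first dose. Section 6.1.1 names no CD24Fc dose, Table 2 names only 480/240/240 mg, and the report in 6.6 decides between continuing and terminating. Section 4.1 does not give the Day 14 and Day 28 doses at a reduced level, and the 120 mg level has no schedule anywhere.

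**4. How likely is the 4.1 trigger?** Inputs: n = 6 (section 10.3); the trigger read as at least 2 patients with a DLT; true DLT rate p assumed. The formula is P(X ≥ 2) = 1 − (1 − p)^6 − 6p(1 − p)^5.

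- p = 0.05: 1 − 0.7351 − 0.2321 = 0.0328, or 3.3%
- p = 0.10: 1 − 0.5314 − 0.3543 = 0.1143, or 11.4%
- p = 0.20: 1 − 0.2621 − 0.3932 = 0.3446, or 34.5%

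**The case against.** On the main point, the best defense is that the specific rule prevails over the general one. Section 4.0 cites 4.1 beside removal and 6.4 beside modification, and items 3 and 4 of 4.1 spare uncomplicated grade 3 neutrophil or platelet falls lasting a week or less. So removal might be meant for DLT-type events and 6.4.3 for brief ones. That may well be the intent, but the text does not say it. Section 4.0 names hematologic toxicity in its own stop rule, and its pointer to 6.4 states neither an exception nor a priority. Section 6.4.3 also has no upper grade limit, so giving it priority outright would keep on drug a patient with a grade 4 hematologic event, which 4.1 treats as a DLT whatever its duration.

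Two stronger readings of the main point are not supported. A reader might take 240 mg as the difference in every case; it is a maximum, as step 2 shows. A reader might also take the 42 planned CD24Fc patients (6 + 36) as the number affected. That is the number covered by the rules, and the documents give no frequency of related hematologic toxicity in this population.

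On the secondary point, the objection carries more weight. De-escalating until a level is cleared has little purpose unless the next phase uses that level. Table 1 has the same header as Table 2, and 4.1 plainly modifies it. A reader might infer that the plan intends Phase II to return to a dose that Phase I rejected. The documents do not show that: this is an omission, Figure 2 is not visible, and 6.6, 6.9, 10.4 and the monthly DSMC review can all stop the trial. What stands is that none of these sets a dose.

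A reader might also infer from the transplant data in 1.4.1 that the trigger has a 9.4% or 20.0% chance. Those figures come from one-sided 95% upper bounds on 0/32 and 1/32 (8.9% and 14.0%), not from estimates. The point estimates give 0% and about 1.3%, in a different population and under a different DLT definition. The 20-30% in 10.3 is no better a source: it is a hypothetical rate used to justify the sample size, for an endpoint defined differently from the 4.1 list.

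Nor is 240/240/240 mg a documented option for the 240 mg level. The only schedule in the protocol that starts at 240 mg is the one in 6.4.3, although 4.1 does not refer to it.

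**Conclusion.** The main point holds on the text alone. Sections 4.0 and 6.4.3 cannot both be followed for related grade 3 or higher hematologic toxicity that recovers in under 2 weeks. The consequence is removal with 0 mg more, against continuation with at most 240 mg after dose 1. It should be fixed because it is a treatment instruction that applies in both phases.

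The carry-forward gap also holds on the visible text, but it is secondary and contingent on at least 2 of 6 Phase I patients having a DLT. Its chance, 3.3% to 34.5%, depends entirely on the assumed DLT rate of 5% to 20%, and it rests on Figure 2 not supplying the missing condition. Neither point changes the sample size or power calculation.

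**What to change.** **Toxicity rule.** Choose one of two options.

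- Let 4.0 govern: delete 6.4.3 and the two-week criterion in 6.7.
- Keep dose reduction: except from 4.0 only related grade 3 hematologic toxicity that meets none of the 4.1 DLT criteria and recovers to grade 1 or less within 2 weeks. Limit 6.4.3 to that case and to doses still to be given, and align 6.7, including recovery in exactly 2 weeks. Because 4.1 is headed Phase I and has a 14-day window, say that its criteria apply here in both phases and after any dose. A broader exception would let grade 4 or other DLT-type events continue on drug.

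**Phase II dose.** State in 6.1.1 and Table 2 that Phase II uses the level cleared under 4.1, and have the 6.6 report name it. Give the Day 1, 14 and 28 doses for each reduced level in 4.1 (for example 240/120/120 mg, as in 6.4.3), or delete the 120 mg level. If any 120 mg dose is kept, add it to 3.0.2, which lists only 480 mg and 240 mg preparations.

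**Cost.** A few sentences in a protocol amendment, plus sponsor decisions on which toxicity rule governs and on the reduced schedules. No added patients, visits or procedures.

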Primary Objective:	Phase I study: To determine the safety and tolerability of CD24Fc in patients with advanced solid tumors who have treatment interruption due to grade 2 or 3 irAEs (by NCI CTCAEv5.0) from immune check point inhibitors (ICIs). Phase II randomized double-blind placebo controlled study: To determine if CD24Fc shortens the recovery time and increases recovery rate of irAEs in cancer patients with grade 2 or 3 irAEs.
Secondary Objectives	Phase I study: Time to irAE reduction by at least 1 grade from CD24Fc. To estimate the time to all irAEs reduced to grade ≤ 1 . Time to resume ICI treatment from the initiation of CD24Fc. To estimate the recovery rate as defined by reduction on irAE by at least one grade. To determine if CD24Fc treatment changes the levels of inflammatory markers in the plasma. Phase II study: To estimate the time to all irAEs reduced to grade ≤ 1 . To record the use of steroids (drug, dose, duration) and other treatment for irAE. To estimate the preliminary overall response rate (ORR), progression free survival (PFS), and 1-year overall survival (OS) after treatment with or without CD24Fc. To determine if CD24Fc treatment changes the levels of inflammatory markers in the plasma
Study Design and Investigational Plan / Methodology:	Phase I study: Patients with advanced solid tumors who have treatment interruption due to grade 2 or 3 irAEs from ICI will be treated with CD24Fc along with standard of care (SOC) treatment for irAE. Phase II randomized double blind placebo controlled study: Patient with advanced solid tumors who have treatment interruption due to grade 2 or 3 irAEs will be randomized (1:1) to receive CD24Fc vs placebo in addition to SOC treatment for irAE. Patient will be stratified randomized by study statistician based on whether steroid was used for irAE at enrollment. Placebo is 100 ml normal saline, which is used to dilute CD24Fc.

Study Schema: Phase I	
Patients with advanced solid tumors who have treatment interruption due to grade 2 or 3 irAEs
 
Study Schema: Phase II	
Patients with advanced solid tumors who have treatment interruption due to grade 2 or 3 irAEs
 
 • Steroids used at registration • No steroids use at registration 
Study Population and Sample Size:	Cancer patients who have treatment interruption due to grade 2 or 3 irAEs on ICI therapy. Phase I: n=6; Phase II: n=72

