6.8 Replacement of Removed Patients

Additional patients are allowed to replace patients who choose to withdraw from the study before or within 28-day course of drug administration or patients who were withdrawn from the study at the investigator's discretion. Patients who are removed due to CD24Fc related DLT will not be replaced.

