10.3 Sample Size Justification

Phase I study: We plan to enroll 6 patients in the phase I study. The objective of this phase I study is to confirm the safety of CD24Fc in ICI-treated cancer patients who have treatment interruption due to grade 2 or 3 irAEs and to estimate the median time to recovery and resumption of ICI after treatment interruption due to irAE. The primary endpoint is new AE of \geq grade 3 that are outside the spectrum of irAEs when CD24Fc is given to treat irAEs. We expect the rate of this event will be less than 33.3%. With a sample size of 6 patients, we would have 74-91% chance to observe at least one occurrence if the true event rate is 20-30%. Hence the sample size is adequate for this pilot study for safety.

Randomized phase II study: Previous studies suggested that recovery rate at 42 days for control group will be about 50% [22, 56]. We hypothesize CD24Fc will increase recovery rate from 50% to 80 %. A sample size of 72 patients (36 in each arm) will have 81% power to detect an increase of response rate from 50% of control group to 80% of CD24Fc group. This result is based on one-sided Fisher's Exact test and significance level of 0.05.

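### The Phase I dose-reduction rule gives no action for 2 of 6 DLTs at the lowest reduced level, can give two actions for 3 or more at the 240 mg first dose, and needs patients that the planned six do not provide

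*Combined protocol and SAP*

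**What the plan says.** The rule is in the closing paragraph of Section 4.1.

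- Window: "The DLT monitoring period is the 14 days after the first dose of CD24Fc at 480 mg".
- Trigger at the starting level: "If DLT occurred in 2 patients during the first dose of CD24Fc dosing in the 14-day period".
- Consequence and acceptance criterion: "CD24Fc will be reduced to 240 mg as first dose, or 120 mg until no more than 1/6 patients developed DLT".
- Termination: "The study will be terminated if >2 patients have DLT at this reduced dosing".

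The size of Phase I is given in several places. The synopsis has "Phase I: n=6; Phase II: n=72" and Section 10.3 has "We plan to enroll 6 patients in the phase I study". Section 6.1.0 likewise refers to six patients in all. Section 6.6 places the report that decides whether the study continues "after the 6th patient (phase I study) has received his/her 3th dose will be prepared". Section 6.8 adds: "Patients who are removed due to CD24Fc related DLT will not be replaced".

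Section 6.4.3 describes a reduction of one level, to 240 mg on day 1 and 120 mg on days 14 and 28. It is triggered by haematologic toxicity, not by the DLT count, but it is the only complete reduced regimen in the documents.

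**The concern.** The acceptance and termination counts at a reduced level do not meet. Acceptance ends at 1 of 6 and termination starts at 3, so a count of 2 falls between them. Where a lower level exists, 2 can be read as a further step down. At the lowest level there is nowhere to go.

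The two sentences can also overlap. If 240 mg and 120 mg are successive levels, 3 or more at 240 mg fails the acceptance criterion, which points to 120 mg, and also passes the termination count.

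The criterion of 1 in 6 presumes six patients at the reduced level, and no section provides them.

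This rule protects patients and determines which regimen can go forward. It is needed only once toxicity has appeared. Two teams with the same data could then stop or continue, and both could cite Section 4.1.

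**Working it through.** **The plan's own figure.** Section 10.3 supports n=6 by a 74-91% chance of at least one event at true rates of 20-30%. With 1 − (1 − p)^6, p = 0.20 gives 73.8%, which agrees. p = 0.30 gives 88.2%, not 91%; 91.2% results at p = 0.333. This figure concerns a single cohort of six and says nothing about a reduced-dose cohort.

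**Actions by DLT count, as written.**

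| DLTs in 6 | Three levels: 240 mg | Three levels: 120 mg | One reduced level only |
|---|---|---|---|
| 0-1 | accept | accept | accept |
| 2 | reduce to 120 mg | none stated | none stated |
| 3-6 | reduce and terminate | terminate | terminate |

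The three-level reading takes 240 mg and 120 mg as successive first doses. The one-reduced-level reading takes the reduced dosing as a single regimen, as in Section 6.4.3.

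**Assumptions for the probabilities (not document figures).** The DLT rate p is the same at every level, each level is judged on six patients, and 2 or more DLTs trigger reduction. Section 4.1 says 2 at the starting level and does not mention 3 or more. The rates 20% and 30% are the range in Section 10.3, and 33.3% is the ceiling it expects not to reach.

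**Formulas**, with X ~ Binomial(6, p):

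- a = P(X ≥ 2) = 1 − (1 − p)^6 − 6p(1 − p)^5
- b = P(X = 2) = 15p²(1 − p)^4
- c = P(X ≥ 3) = a − b

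At p = 0.20: a = 1 − 0.2621 − 0.3932 = 0.345, b = 15 × 0.04 × 0.4096 = 0.246, c = 0.099.

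| Quantity | Formula | 20% | 30% | 33.3% |
|---|---|---|---|---|
| Second cohort needed | a | 34.5% | 58.0% | 64.9% |
| Exactly 2 DLTs, given the level is reached | b | 24.6% | 32.4% | 32.9% |
| 3 or more DLTs, given the level is reached | c | 9.9% | 25.6% | 32.0% |
| Three levels: conflict at 240 mg | a × c | 3.4% | 14.8% | 20.7% |
| Three levels: gap at 120 mg | a × a × b | 2.9% | 10.9% | 13.9% |
| Same, if 3 or more at 240 mg terminates | a × b × b | 2.1% | 6.1% | 7.0% |
| One reduced level: gap there | a × b | 8.5% | 18.8% | 21.4% |
| Expected Phase I size, three levels | 6 + 6a + 6a² | 8.8 | 11.5 | 12.4 |

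**Size and time.** The path needs 6 patients without a reduction, 12 with one, and 18 with two if there are two reduced levels. At the synopsis accrual of 4-5 per month, 12 patients take 12/5 to 12/4 = 2.4 to 3.0 months and 18 take 3.6 to 4.5 months, for accrual alone. The synopsis allows about 3 months for Phase I.

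**The case against.** **The conflict depends on reading.** If the reduced dosing in the termination sentence means only the lowest level, or if termination overrides reduction, 3 or more at 240 mg has one action. That is correct, but the text says neither. Section 6.4.3 and the singular wording of the termination sentence lend some support to a single reduced level. The conflict then goes and the maximum is 12, but the gap at 2 of 6 moves to that level. A maximum of 18 is therefore one reading, not a fact of the plan.

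**The chance may be small.** A reader might take the 25-33% for exactly 2 of 6 as the chance that the trial meets the gap. It is conditional on having reached that level; the figures from study start are lower. They also assume that the DLT rate does not fall with dose. Section 1.4.1 reports no DLTs in 18 CD24Fc patients, though in a transplant population. At a true rate of 10% a second cohort is needed in 11.4% of trials, and on the three-level reading the conflict and the gap arise in about 0.2% and 0.1%.

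**A stop at 3 of 6 might look too lax against the 33.3% limit in Sections 10.3 and 10.4.** The documents do not support this inference. It compares an observed count with a limit on a true rate. With the Section 10.4 toxicity prior, Beta(0.3, 1.7), 3 of 6 gives Beta(3.3, 4.7) and a posterior probability of 0.66 that the rate exceeds 0.333. For 4 of 6 it is 0.88 and for 5 of 6 it is 0.973, the first to pass 0.97. The Section 10.4 table accordingly stops at 5 or more with 12 enrolled, six of them on CD24Fc. Section 4.1 is the stricter rule. Nor is it inconsistent that 2 DLTs trigger a reduction at 480 mg but do not stop the study at a reduced dose, since these are different actions.

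**There are backstops.** The Section 6.6 report addresses continuation, and under Section 13.0 the monitoring committee meets monthly and reviews adverse events. An unlisted count would reach someone. Neither has a numerical criterion, so neither fills the gap.

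**Conclusion.** The point holds. Two parts are firm on either reading of the levels: exactly 2 of 6 at the lowest reduced level has no action, and a Phase I of 6 covers one cohort only. The double action at 240 mg holds on the plain reading only.

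The size shortfall is the most probable consequence, because it follows any first cohort with 2 or more DLTs. The gap and the conflict are less frequent from study start and depend on the assumed rate and the number of levels. Their importance lies in what the rule governs: it fails when followed as written, in the situation it exists to handle. No conclusion is drawn about whether the stop count is too high or too low.

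**What to change.** In Section 4.1, reconcile the acceptance and termination sentences so that every DLT count from 0 to 6, at every level the sponsor intends, leads to exactly one action. State whether 240 mg and 120 mg are successive first-dose levels or parts of one reduced regimen, and align this with Section 6.4.3. Give the denominator for the termination count, say what happens with more than 2 DLTs at the starting level, and define the DLT window for a reduced first dose, since it is now defined only for 480 mg.

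In the synopsis and Sections 6.1.0 and 10.3, restate the Phase I size as 6 plus six per reduced cohort, with a maximum of 12 or 18 according to the number of levels. In Section 6.6, tie the report to the last patient of the accepted cohort. The counts and doses are for the sponsor to choose.

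The cost is protocol wording and a size stated as a range. Extra patients, and possibly a longer Phase I, arise only in the reduction that Section 4.1 already foresees.
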